#### 4.2.2. Study Drug Compliance

Compliance will be calculated for study drugs VBR, ETV and Peg-IFN $\alpha$ .

The total number of tablets (VBR and ETV) and injections (Peg-IFN $\alpha$ ) administered will be summarized by treatment phases using descriptive statistics.

The presumed total number of tablets (VBR and ETV) administered to a subject will be determined by the data collected on the Drug Accountability- ABI-H0731 and ETV CRFs respectively using the following formula:

$$\begin{aligned} \text{Total Number of Tablets Administered} = \\ \left( \sum \text{No. of Tablets Dispensed} \right) - \left( \sum \text{No. of Tablets Returned} \right) \end{aligned}$$

The presumed total number of injections (Peg-IFN $\alpha$ ) administered to a subject will be determined by the data collected on the Drug Accountability- Peg-IFN $\alpha$  CRF using the following formula:

$$\begin{aligned} \text{Total Number of Doses Administered} = \\ \left( \sum \text{No. of Syringes Dispensed} \right) - \left( \sum \text{No. of Syringes Returned} \right) \end{aligned}$$

##### 4.2.2.1. On-Treatment Compliance

The level of on-treatment compliance to the study drug will be determined by the total amount of study drug administered relative to the total amount of study drug expected to be administered during a subject's actual on-treatment period.

The level of on-treatment compliance for each study drug will be expressed as a percentage using the following formula:

$$\text{On-Treatment Compliance (\%)} = \left( \frac{\text{Total Amount of Study Drug Administered}}{\text{Total Amount of Study Drug Expected to be Administered On Treatment}} \right) \times 100$$

Per protocol, each subject completing treatment and receiving VBR is expected to take three 100 mg tablets of VBR daily during the Randomized Treatment Phase (ie, a total of 504 tablets is expected in a 24-week period) and during the Overall Treatment Phase (ie, a total of 1008 tablets are expected in a 48-week period). Each subject completing treatment and receiving ETV is expected to take a single oral 0.5 mg tablet once daily during the Randomized Treatment Phase (ie, a total of 168 tablets is expected in a 24-week period), during the Overall Treatment Phase

(ie, a total of 336 tablets are expected in a 48-week period). Each subject completing treatment and receiving Peg-IFN $\alpha$  is expected to have a total of 24 syringes of Peg-IFN $\alpha$  administered.

For subjects who prematurely discontinue, the denominator will be the total amount of study drug expected to be administered by the date of premature discontinuation.

Descriptive statistics for the level of on-treatment compliance with the number and percentage of subjects belonging to compliance categories (eg, <=80%, > 80-90%, and  $\geq$  90%) will be provided by treatment group for the Safety Analysis Set.

A by-subject listing of study drug administration and drug accountability will be provided separately by subject ID number in ascending order and visit in chronological order.

#### **4.3. Protocol Deviations**

Subjects who did not meet the eligibility criteria for study entry but enrolled in the study will be summarized. The number and percentage of subjects who did not meet at least 1 eligibility criterion will be provided for specific criteria by treatment group based on the All Randomized Analysis Set. A by-subject listing will be provided for those subjects who did not meet at least 1 eligibility (inclusion or exclusion) criterion. The listing will present the eligibility criterion (or criteria if more than 1 deviation) that subjects did not meet and related comments, if collected.

Protocol deviations (PDs) occurring after subjects entered the study are documented during routine monitoring. The number and percentage of subjects with important PDs (IPDs) by deviation category will be summarized by treatment group for All Randomized Analysis Set. A by-subject listing will be provided for those subjects with any PDs.

A table will be provided to summarize any COVID-19 related PDs with the deviation reason by treatment groups. Any visits that were not performed will be summarized by reason (ie, adverse event, COVID-19 restrictions, and Other). A listing of subjects who had study disruption due to COVID-19 will be provided with a description.

## 5. BASELINE CHARACTERISTICS

### 5.1. Demographics and Baseline Characteristics

Subject demographic variables (i.e., age, age group [ $<50/\geq 50$  years], sex, race, and ethnicity), baseline characteristics (body weight [in kg], height [in m], body mass index [BMI; in kg/m^2]) will be summarized by treatment group and overall using descriptive statistics for continuous variables and using number and percentage of subjects for categorical variables. The summary of demographic data will be provided for the Safety Analysis Set.

A by-subject demographic listing, including the informed consent date, will be provided by subject ID number in ascending order.

### 5.2. Baseline Disease Characteristics

Baseline disease characteristics will be summarized by treatment group and overall. Descriptive summary statistics will be used for continuous variables and the number and percentage of subjects will be used for categorical variables. The following factors will be included, but not limited to:

- Years positive for HBV
- HBV Genotype
- Baseline HBV DNA ( $\log_{10}$  IU/mL)
- Baseline HBV pgRNA ( $\log_{10}$  U/mL)
- Baseline HBeAg ( $\log_{10}$  IU/mL)
- Baseline HBcrAg ( $\log_{10}$  kU/mL)
- Baseline HBsAg ( $\log_{10}$  IU/mL)
- Baseline HBeAg antibody (HBeAb)
- Baseline HBsAg antibody (HBsAb)
- Baseline antibody to the HBV core-related antigen (HBcrAb)
- Baseline ALT (U/L)
- Baseline ALT group ( $>\text{ULN}$  [Covance],  $>\text{ULN}$  [American Association for the Study of Liver Diseases (AASLD)])

- Baseline ALT group ( $<5 \times \text{ULN}$ ,  $\geq 5 \times \text{ULN}$ )
- Liver biopsy staging
- Fibroscan result
- Metavir Fibrosis Stage

A by-subject listing of baseline disease characteristics will be provided by subject ID number in ascending order.

### **5.3. Medical History**

Medical history collected at screening will be coded using the Medical Dictionary for Regulatory Activities (MedDRA) Version (v) 23.1.

Medical history will be summarized by preferred term (PT), treatment group and overall. Subjects who report 2 or more medical history items that are coded to the same PT will be counted only once by the unique coded term in the summary. The summary will be provided for the Safety Analysis Set.

HBV-specific medical history will be summarized by mode of HBV infection, treatment group and overall. The summary will be provided for the Safety Analysis Set.

A by-subject listing of medical history will be provided by subject ID number in ascending order.

## 6. EFFICACY ANALYSES

The primary analysis set for efficacy analyses will be the FAS, defined in [Section 3.1.2](#). All the efficacy analyses will be performed for each cohort separately.

### 6.1. Efficacy Endpoints

#### 6.1.1. Definition of Primary Efficacy Endpoints

The efficacy endpoints include the following:

- Mean change in  $\log_{10}$  HBV DNA from Baseline at each timepoint
- Mean change in  $\log_{10}$  HBV pgRNA from Baseline at each timepoint
- Mean change in  $\log_{10}$  serum viral antigens (ie HBcrAg, HBeAg, and HBsAg) from Baseline at each timepoint

#### 6.1.2. Primary Analysis for Primary Efficacy Endpoints

The observed and mean change in  $\log_{10}$  HBV DNA, HBV pgRNA, HBcrAg, HBeAg and HBsAg from Baseline will be summarized using descriptive statistics (sample size, mean, SD, median, Q1, Q3, minimum, and maximum) by treatment group.

The comparison in change from baseline between treatment groups will be performed using the analysis of covariance (ANCOVA) model, including baseline value, the stratification factors, and treatment group as covariates. The estimated least square means of treatment effects and estimated difference in treatment effects between treatment groups will be presented along with the 95% CIs and p-values. The analysis will be based on observed data only. No imputation will be done for missing data.

## 6.2. Changes From Protocol-Specified Efficacy Analyses

Since the study is terminated early, the efficacy analyses for the key secondary and other secondary endpoints specified in the protocol will not be performed.

## 7. SAFETY ANALYSES

### 7.1. Adverse Events and Deaths

#### 7.1.1. Adverse Event Dictionary

Clinical and laboratory adverse events (AEs) will be coded using the Medical Dictionary for Regulatory Activities (MedDRA) Version (v) 23.1. System organ class (SOC), high-level group term (HLGT), high-level term (HLT), preferred term (PT), and lower-level term (LLT) will be provided in the AE dataset.

#### 7.1.2. Adverse Event Severity

Adverse events are graded by the investigator as Grade 1, 2, 3, or 4 according to the toxicity criteria specified in the protocol. The severity grade of events for which the investigator did not record severity will be categorized as “missing” for tabular summaries and data listings. The missing category will be listed last in summary presentation.

#### 7.1.3. Relationship of Adverse Events to Study Drug

Related AEs are those for which the investigator selected “Related” on the AE CRF to the question of “Relationship to Study Treatment” based on his/her clinical assessment. Events for which the investigator did not record relationship to an applicable study drug will be considered related to study drug for summary purposes. However, by-subject data listings will show the relationship as missing.

#### 7.1.4. Serious Adverse Events

Serious adverse events (SAEs) will be identified and captured as SAEs if the AEs met protocol-specified definitions of a SAE.

#### 7.1.5. Treatment-Emergent Adverse Events

##### 7.1.5.1. Definition of Treatment-Emergent Adverse Events

Treatment-emergent adverse events (TEAEs) are defined as any AEs with an onset date/time equal to or after the date/time of first dose of study drug and no later than 28 days after the last dose date of any study drug.

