## 1. SYNOPSIS

**Protocol Number:** ABI-H0731-203

**Title:** A Randomized Phase 2a, Multicenter, Open-label Study Evaluating ABI-H0731-Containing Regimens in Patients with Chronic Hepatitis B

**Phase:** 2a

**Number of Subjects:** Approximately 60

**Study Duration:** Up to 45 days for Screening, 48 weeks of treatment and 12 weeks of follow-up

**Rationale:** Chronic hepatitis B (CHB) is a major cause of liver-related morbidity and mortality worldwide. ABI-H0731 (731) is an orally administered, direct-acting antiviral agent targeting the hepatitis B virus (HBV) core protein. Through its interaction with core protein, 731 interferes with multiple steps in the viral lifecycle including early events (capsid disassembly and DNA delivery to the nucleus for formation of covalently closed circular [cccDNA]) and late events (assembly of pregenomic (pg) RNA-containing capsids which are required for HBV replication). ABI-H0731 may also prevent newly formed DNA-containing nucleocapsids from delivering HBV DNA to the nucleus to amplify the pool of cccDNA in infected cells. Entecavir (ETV) is an approved, orally administered direct-acting antiviral that inhibits the reverse transcription of HBV pgRNA to DNA. Pegylated (Peg)-interferon alpha (IFN $\alpha$ ) is an approved, subcutaneously administered biologic which has both antiviral and immunomodulatory activities. While the specific mechanisms by which Peg-IFN $\alpha$  exerts its antiviral activity against HBV are not fully understood, it is thought to inhibit multiple steps in the viral lifecycle and to augment the host immune response. The combination of 731 with ETV and Peg-IFN $\alpha$  will provide multiple complementary antiviral mechanisms that may act synergistically to increase CHB cure rates. It is anticipated that the combination of 731 and ETV with or without Peg-IFN $\alpha$  will be safe, reduce viral nucleic acids (ie, HBV pgRNA and HBV DNA) and reduce viral antigens (ie, hepatitis B “e” antigen [HBeAg], hepatitis B core-related antigen [HBcrAg], and hepatitis B surface antigen [HBsAg]) in subjects with CHB. This Phase 2a study will explore the safety of the 731+ETV+Peg-IFN $\alpha$  combination, its antiviral activity, as measured by effects on serum HBV pgRNA, HBV DNA, and HBV antigens, and pharmacokinetics (PK).

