# 8. ADVERSE EVENTS

An AE is any untoward medical occurrence in a study subject administered an investigational product(s) regardless of the causal relationship with treatment.

An AE, therefore, can be any unfavorable and unintended sign (including laboratory finding), symptom, or disease temporally associated with participation in an investigational study, whether or not considered drug related. In addition to new events, any increase in the severity or frequency of a pre-existing condition that occurs after the subject signs the ICF for participation is considered an AE. This includes any side effect, injury, toxicity, or sensitivity reaction.

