## 8.1. Documenting Adverse Events

Adverse events will be monitored throughout the entire study. Investigators will ask the subject at each visit if they have experienced any untoward effects since the last study visit. All AEs (for all randomized subjects and excluding screen failures) will be entered in the electronic case report form (eCRF) provided: a description of the event, severity, time of occurrence, duration, any action (eg, treatment and follow-up tests), and the outcome should be provided along with the Investigator's assessment of the relationship to the study treatment.

Adverse events will be recorded from the date informed consent is signed through the end of study (completion of follow-up period or if the subject is lost to follow-up).

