#### **10.3.6.1. Treatment-emergent Adverse Events**

Treatment-emergent adverse events reported during the study will be coded using the Medical Dictionary for Regulatory Activities (MedDRA) dictionary. Incidence of TEAEs will be summarized by treatment group and the following:

- Preferred term
- System organ class and preferred term
- System organ class, preferred term, and severity

These summaries will be presented for the following TEAE categories:

- All AEs
- SAEs
- Drug-related AEs

For tables reporting adverse events by severity, if a subject has multiple occurrences of an AE with the same system organ class and preferred term, the most severe event will be presented.

All AEs will be recorded from the first dose of study drug (731, ETV, or Peg-IFN $\alpha$ ) until the last study visit.

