#### **7.2.1.1.      Treatment-Emergent Laboratory Abnormalities**

Treatment-emergent laboratory abnormalities are defined as values that increase at least 1 toxicity grade from Baseline at any postbaseline time point, up to and including the date of last dose of any study drug plus 28 days for the Overall Treatment Phase. For the Randomized Treatment Phase, the treatment-emergent laboratory abnormalities will be summarized up to the last dose at Week 24.

If the relevant baseline laboratory value is missing, any abnormality of at least Grade 1 observed within the time frame specified above will be considered treatment emergent.

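### The TEAE definition has no worsening criterion, so an AE that starts before first dose and worsens on treatment can drop out of the TEAE tables, depending on a recording rule the documents do not state

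*Combined protocol and SAP*

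**What the plan says.** - **TEAE definition (SAP 7.1.5.1).** TEAEs are "any AEs with an onset date/time equal to or after the date/time of first dose of study drug". The window closes 28 days past the final dose. Both limits refer to onset.
- **Incomplete dates (SAP 7.1.5.2).** The rule again works from onset. Stop dates matter only when the onset is incomplete or missing.
- **AE tables (SAP 7.1.6).** All on-treatment tables are restricted to TEAEs: overall, by grade, related to each drug, serious, and leading to stopping a drug or the study. The follow-up table takes only AEs later than 28 days after the last dose. One listing shows all AEs.
- **What counts as an AE (Protocol 8).** Besides new events, an "increase in the severity or frequency of a pre-existing condition that occurs after the subject signs the ICF for participation is considered an AE".
- **When recording starts.** Protocol 8.1: "Adverse events will be recorded from the date informed consent is signed through the end of study". Protocol 10.3.6.1: "All AEs will be recorded from the first dose of study drug". The time between consent and first dose can be long, since the synopsis allows "Up to 45 days for Screening".
- **Laboratory part (SAP 7.2.1.1).** Treatment-emergent abnormalities are "values that increase at least 1 toxicity grade from Baseline at any postbaseline time point", so worsening is counted.
- **Discontinuation part (SAP 4.1).** Non-completion of each drug, with reasons, is tabulated whatever the TEAE status of the event.

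**The concern.** The primary endpoint (Protocol 3.2.1) is a safety endpoint, and its AE part is reported through the TEAE tables. Suppose a subject reports Grade 1 insomnia or headache during Screening, and it reaches Grade 3 after dosing starts. Aggravation of that kind is something a tolerability table should show. Under an onset-only rule, whether it is shown depends on how the site entered it: as a change to the existing record, or as a new event.

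The same would apply to an event that becomes serious or leads to stopping a drug. Its row in the serious, related or leading-to-discontinuation table would be one subject short. With small groups and purely descriptive reporting, a reader has little except those rows to go on.

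**Working it through.** There is no stated figure to reproduce. The sample size has no statistical basis (Protocol 10.1), and the point concerns a definition. The check is a trace of one AE, with onset after consent and before first dose, that worsens on treatment.

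1. **Single record, complete pre-dose onset date.** It fails the start rule in SAP 7.1.5.1, so it is in no TEAE table. Its onset is not after the follow-up cut-off, so it is not in the follow-up table. It appears only in the all-AE listing.
2. **Worsening entered as a new AE under Protocol 8.** Its onset is the date of worsening, which is after first dose. It is a TEAE and is counted.
3. **Partial onset date in the month of first dose, stop date not before first dose.** It is counted under SAP 7.1.5.2.
4. **Missing onset, stop date after first dose.** It is counted under SAP 7.1.5.2.

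So an AE of unknown onset is counted, while one with a known Screening onset and documented on-treatment worsening may not be.

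Which of cases 1 and 2 applies is not settled:

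- Protocol 8 speaks of a pre-existing condition and does not say whether an AE that itself began after consent is one.
- Protocol 8.1 asks for one severity, time of occurrence and duration per event, and Protocol 8.7 has each AE followed to resolution. Both fit a single record, but neither addresses a grade change.
- Protocol 7.3 has medical history updated before dosing on Day 1, and Protocol 10.3.6.1 starts AE recording at first dose. Both fit holding pre-dose events as history, which would make worsening a new AE.

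**Scale.** About 60 subjects randomized 1:1:1 gives 60 / 3 = 20 per group. One missed subject is 1 / 20 = 5 percentage points in that group's row.

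**Illustration with assumed rates (none are in the documents).** Let a be the share of subjects with an AE ongoing on Day 1, and b the share of those whose AE worsens on treatment and stays in a single record. Expected missed subjects = 60 × a × b.

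- Low: a = 10%, b = 10%: 60 × 0.10 × 0.10 = 0.6.
- High: a = 30%, b = 25%: 60 × 0.30 × 0.25 = 4.5.

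The chance of at least one such subject is 1 − (1 − q)^60, where q = a × b. For q = 1%, 2% and 5% it is 45%, 70% and 95%. If sites open a new record for every worsening, q is zero and nothing is lost.

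**The case against.** The strongest reply is that Protocol 8 already handles this: worsening is an AE in its own right, so it would be entered with an on-treatment onset and meet the TEAE definition. That is clear for medical-history conditions. For AEs that began after consent it is one possible reading, and the eCRF and its completion rules, which would decide it, are not part of these documents. A reader might therefore infer that such events are certainly left out of every AE table. The documents do not support that; the loss is conditional on case 1.

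A reader might also infer that the whole primary endpoint is undercounted. It is not. Laboratory worsening is counted under SAP 7.2.1.1 and discontinuations under SAP 4.1, neither of which uses the TEAE definition, and the listing shows every AE. The contrast with the laboratory rule is suggestive only: laboratory tests have a measured Baseline grade, whereas AEs are event records.

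Third, a reader might infer bias against the comparison of interferon and non-interferon groups. Protocol 2.1 lists common interferon side effects, so aggravation of symptoms is plausible in Groups 2 and 3, but no figure shows it. The overall any-TEAE proportion would change only for a subject with no other TEAE, which common side effects make less likely in those groups. The effect is on individual rows.

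Finally, the study was terminated early and the output is a descriptive synoptic report, so no test or stopping rule depends on the definition. That lowers the stakes. It does not remove the gap in the rule.

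**Conclusion.** The point holds in conditional form. The TEAE definition uses onset only, and all on-treatment AE tables depend on it. A pre-dose AE that worsens on treatment and stays in one record with a known pre-dose onset is seen only in the listing. Whether that happens depends on a recording rule the documents do not give, and they disagree on when AE recording begins.

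Relative to a definition that includes worsening, the error can only be an undercount. Its size is unknown: 5 percentage points per missed subject in an affected row, with 0.6 to 4.5 subjects across the trial under the assumed rates. It has no bearing on sample size or on any inferential claim. It is worth correcting because the count of the AE part of the primary endpoint should not rest on an unstated data-entry convention.

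**What to change.** 1. Extend SAP 7.1.5.1 to include AEs with onset before the first dose that increase in severity grade or become serious on or after the first dose, up to the same end date, with the date of worsening used for phase assignment.
2. Before database lock, query Screening-onset AEs still ongoing on Day 1 for the date and grade of any worsening.
3. State whether a grade change opens a new eCRF record. Where sites have already done so, count each worsening once.
4. Reconcile Protocol 8.1 (recording from consent) with Protocol 10.3.6.1 (recording from first dose).

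The cost is one SAP sentence, a short clarification and a small number of queries. TEAE counts may rise slightly. If sites already open a new record for worsening, the counts do not change. SAP Section 1 already provides for documenting changes made after finalization in the synoptic report.

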##### 7.1.5.2. Incomplete Dates

If the onset date of the AE is incomplete and the AE stop date is not prior to the first dose date of any study drug, then the month and year (or year alone if month is not recorded) of onset determine whether an AE is treatment emergent. The event is considered treatment emergent if both of the following 2 criteria are met:

- The AE onset is the same as or after the month and year (or year) of the first dose date of study drug, and
- The AE onset date is the same as or before the month and year (or year) of the date corresponding to 28 days after the date of the last dose of any study drug

An AE with completely missing onset and stop dates, or with the onset date missing and a stop date later than the first dose date of any study drug, will be considered to be treatment emergent. In addition, an AE with the onset date missing and incomplete stop date with the same or later month and year (or year alone if month is not recorded) as the first dose date of any study drug will be considered treatment emergent.

